Subjective Refractive Error Determination: Subjects who meet all inclusion criteria for the study will be enrolled and be fitted in two different kinds of contact lenses throughout the course of the study. Before fitting the contact lenses, a subjective refraction will be performed to determine the best correction and contact lens power for the subject. The refraction will be performed by a licensed, trained optometrist ([name]) using a phoropter. Patient responses will be used to determine the final refractive error. This method is identical to refractive error determination in a regular eye exam.

Contact Lens Fitting: In this crossover trial, single vision Bausch + Lomb ULTRA® contact lenses and Bausch + Lomb ULTRA® for Presbyopia contact lenses will be fitted by a licensed optometrist. Bausch + Lomb ULTRA® and Bausch + Lomb ULTRA® for Presbyopia are FDA-approved daily wear soft contact lenses. All subjects will be habitual soft contact lens wearers, so no increased risk will be assumed by fitting the Bausch + Lomb ULTRA® contact lenses.

Anterior Ocular Segment Assessment: While the risk of contact lens complications (ocular inflammation, infection, etc.) in this study is extremely low, the anterior segment ocular health of both eyes of every subject will be assessed by a licensed optometrist at each visit to ensure no complications have occurred. This assessment will also include the ocular adnexa (lid margin and Meibomian glands). In the unlikely event that a complication does occur, the subject will be treated by a licensed optometrist and dismissed from the study.

c. Detailed Study Procedures

Overview

This randomized, prospective, crossover clinical trial will recruit uncomfortable, single vision, soft contact lens wearers in the non-presbyopic age range. The tenants of the Declaration of Helsinki will be followed. Complete inclusion criteria are listed in Table 1. Each subject will receive a single vision (Bausch + Lomb ULTRA®) and multifocal contact lens (Bausch + Lomb ULTRA® for Presbyopia) to wear for 2 weeks each. Subjects will be masked and randomly assigned to the first lens and then they will be crossed over to the remaining lens for the second 2-week period. Figure 1 displays a flow chart of the planned study procedures.

Subject Enrollment and Baseline Examination and Fitting

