Each lens is made in only one size (base curve and diameter), so the main parameter determined during the fitting process will be power of the lens. For the single vision lens and multifocal lens, the power will be determine based on the spherical equivalent of the subject's refractive error. For the multifocal contact lens, subjects will receive a Low Add power in both eyes. Vision, fit, and comfort of the contact lens will be assessed in office on both eyes. Lenses will be allowed to settle on the eye for approximately 10 minutes before vision or fit are assessed. Once a satisfactory fit and visual endpoint has been achieved (patient is comfortable in lenses, binocular vision is better than 20/40, and examiner determines proper contact lens fit), the subject will be instructed to wear the lenses daily for the next 2 weeks. Accommodative testing and heterophoria measurements with the first dispensed lens pair will be performed. Subjects will be instructed not to sleep in the contact lenses and to remove them each night to clean and soak and Biotrue® contact lens solution. A clean contact lens case and Biotrue® solution will be provided to each subject. Subjects will be given the contact information of the PI and instructed to contact investigators if they experience any signs of complications (redness, discharge, irritation, pain, etc.). Before leaving the baseline examination, each subject will schedule an appointment for the second examination approximately 2 weeks from the initial baseline examination date (no sooner than 2 weeks, no later than 3 weeks). The Bausch + Lomb ULTRA® contact lenses are FDA-approved for daily wear. Subjects will receive \$40 cash and a parking pass at the end of the baseline examination.

[figure not shown]

Figure 1: Flow chart of study procedures for randomized crossover clinical trial (Please see Data Analysis and Sample Size Justification section for updated sample size numbers)

Second Examination and Fitting

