Subjects will be asked which of the two trial lens pairs they preferred and be asked which lens (single vision or multifocal) they think they had first and second. After all testing and procedures have been completed, subjects will be instructed to return to habitual contact lens wear and informed of what lenses they had during the first and second trial periods. Subjects will receive \$40 cash and a parking pass at the end of the third examination.

Data Analysis and Sample Size Justification

Paired *t* tests will be performed to compare mean CLDEQ-8 scores with habitual single vision lenses, single vision Bausch + Lomb ULTRA® contact lenses, or Bausch + Lomb ULTRA® for Presbyopia contact lenses to one another. Repeated measures ANOVA testing will be performed to determine if contact lens comfort (CLDEQ-8 score) is affected by age or magnitude of myopia when subjects are corrected with their habitual single vision lenses, single vision Bausch + Lomb ULTRA® contact lenses, or ULTRA® for Presbyopia contact lenses. CISS scores throughout the trial will be analyzed in the same way as the CLDEQ-8 scores. To determine if accommodative ability is related to multifocal preference, paired *t* tests will be used to compare contact lens preference (single vision versus multifocal) to initial accommodative function (lag/lead) values.

In order to detect a conservative standardized effect size of 0.6 ($\alpha = 0.05$, $\beta = 0.20$), a sample size of 45 subjects would be necessary. A previous cross-over trial utilizing the CLDEQ-8 reported a 20% loss-to-follow-up rate.¹¹ Anticipating and accounting for a similar rate in our subject enrollment, a sample of 54 subjects would be appropriate. Because the hypotheses of this study have never been tested, we recognize that this initial sample size may seem inadequate after all data is collected. So, our initial 54-subject sample size will be increased by an additional 25% to allow for additional data collection that may be necessary. Therefore, 68 subjects (34 subjects per group) will be sought for IRB approval to account for the possibility of needing more subject data to make reliable study conclusions.

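### The study-lens contrast uses completers only although about 20% loss is expected; if loss is unequal between lenses and related to discomfort, it can favour the lens that caused more of it

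*Combined protocol and SAP*

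**What the plan says.** All references are to the combined protocol and SAP.

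- **Expected loss.** Data Analysis and Sample Size Justification: "A previous cross-over trial utilizing the CLDEQ-8 reported a 20% loss-to-follow-up rate". The response is a larger sample: "Anticipating and accounting for a similar rate in our subject enrollment, a sample of 54 subjects would be appropriate". No split by lens or by cause is given.
- **Analysis.** The same section compares mean CLDEQ-8 on the habitual, single vision and multifocal lenses pairwise by paired t tests, and treats CISS in the same way. The document gives no missing-data method, analysis population or sensitivity analysis.
- **When scores are taken.** Second Examination and Fitting, and Third and Final Examination: CLDEQ-8 and CISS for the lens just worn are given at these two visits. In both lists they come before lens removal and the anterior segment check. Neither section provides for a score at early exit or for recording the reason and lens.
- **Fitting.** Subject Enrollment and Baseline Examination and Fitting: randomisation is described before fitting, and dispensing follows "Once a satisfactory fit and visual endpoint has been achieved", which includes the subject being comfortable. No rule covers a randomised subject who does not get there.
- **Complications.** Anterior Ocular Segment Assessment: in case of a complication, "the subject will be treated by a licensed optometrist and dismissed from the study". The same paragraph calls the risk extremely low.

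**The concern.** The outcome is lens discomfort, so leaving because a lens is uncomfortable is itself information about the outcome. A paired t test of multifocal against single vision sees only subjects who have a score on both. If one lens drives out more of the people who do badly on it, the remaining subjects are a selected group in which that lens looks better than it would among all those randomised. Enlarging the sample replaces lost precision but leaves this bias untouched. Because neither the lens nor the reason for exit is recorded under the plan, the final report could not show whether it had happened.

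**Working it through.** **1. The plan's own figures.** Inputs: "In order to detect a conservative standardized effect size of 0.6", alpha 0.05, beta 0.20; two-sided testing is assumed.

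- A two-sample t test gives 44.6 per group, matching "a sample size of 45 subjects would be necessary". A paired t test at 0.6 SD of the paired difference needs 24.
- Loss: 45 × 1.20 = 54. (45 / 0.80 = 56.25, so dividing by the retained fraction would give 57.)
- Further 25%: 54 × 1.25 = 67.5, stated as 68.

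**2. Is power the problem?** 54 × 0.80 = 43.2 and 68 × 0.80 = 54.4 complete pairs. Paired power at 0.6 is 97% with 43 pairs and 99% with 54. The loss threatens validity rather than power.

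**3. How many have no pair?** The 11/21/2017 update reports 69 enrolled, 15 of them in the new round that seeks 30. So 69 − 15 = 54, and 54 + 30 = 84. At 20% loss, 84 × 0.20 = 16.8, about 17 subjects without a study-lens pair.

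**4. Which exits lose what?**

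| Exit | Score on that lens scheduled? | Multifocal versus single vision pair |
|---|---|---|
| Never reaches the fitting endpoint, first lens | No | Lost |
| Leaves during period 1 | No | Lost |
| Complication first found at second examination | Yes, first lens | Lost |
| Never reaches the fitting endpoint, second lens, or leaves during period 2 | First lens only | Lost |
| Complication first found at third examination | Yes, both | Kept |

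A lone first-lens score still enters the comparison with the habitual lens, because a habitual CLDEQ-8 is taken at phone screening and a CISS at baseline.

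**5. Size in points (illustration).** Assumptions: a share p = 0.10 leaves because of one lens; these subjects would have scored d = 4 to 8 points worse on it than completers; other losses are unrelated to score; the two lenses have equal SDs; within-subject correlation r is 0.3 to 0.7.

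- Bias in that lens's mean = p × d = 0.10 × 4 to 0.10 × 8 = 0.4 to 0.8 points.
- The same people would be expected to score r × d worse on the other lens, so bias in the paired contrast = p × d × (1 − r):
  - r = 0.3: 0.28 to 0.56
  - r = 0.5: 0.20 to 0.40
  - r = 0.7: 0.12 to 0.24

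**6. Size in SDs of the paired difference.** Simulation with no true lens difference and r = 0.3, 0.5, 0.7. The loss patterns are assumptions.

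| Loss pattern | Bias toward the lens causing more loss |
|---|---|
| 20% at random | 0.00 |
| About 20%, equal across lenses, score-related | 0.00 |
| About 14% through one lens, 5% through the other | 0.03 to 0.05 |
| About 21% through one lens only, moderate dependence on its score | 0.07 to 0.11 |
| Worst 20% on one lens all lost (upper bound) | 0.13 to 0.21 |
| Worst 2% on one lens lost (complications only) | 0.02 to 0.03 |

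**The case against.** The strongest reply is that nothing in the documents shows loss to be lens-related. The 20% is an overall rate from another trial, and loss that is random or equal across lenses produces no bias. Complications are described as extremely rare, and the fitting section does not say that anyone fails or is dropped. Precision is ample. All of this stands, and it makes the direction and size conditional.

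It also rules out several stronger readings that a reader might infer:

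- *That the 20% includes complication dismissals.* The document does not say so. A complication-only scenario gives just 0.02 to 0.03 SD.
- *That no outcome is collected from those who leave.* This fits exits between visits and fitting failures. It does not fit complications first found at a scheduled examination, where the questionnaires are listed first.
- *That a lone first-period score is discarded.* It is lost from the study-lens contrast but still used against the habitual lens.
- *That the contrast is biased by 0.4 to 0.8 points.* That is the bias in one lens's mean. The contrast moves less, because people who do badly on one lens tend to do worse on the other too.

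It is also fair that a mixed model does not cure loss that depends on a score never observed, and that an exit questionnaire cannot reach people who cannot be contacted. What does not stand is that the gap is harmless: the plan expects substantial loss and provides no means to detect or examine lens-related loss.

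**Conclusion.** The point holds as a conditional one. Under the plan, subjects with fewer than two study-lens scores drop out of the multifocal versus single vision contrast, about 17 of 84 if loss is 20%. If that loss is unequal between lenses and related to discomfort, the contrast can favour the lens that caused more of it. On the assumptions in the working, the shift is about 0.12 to 0.56 points, or 0.03 to 0.21 SD of the paired difference when unequal loss is near 20% in total. For scale, 0.12 / 4 = 3% and 0.56 / 4 = 14% of the 4-point difference that the 8/14/2017 update calls clinically significant, though that figure concerns age groups and not lenses. The documents supply no split by lens, no correlation and no score difference for leavers, so neither the presence nor the direction of bias can be asserted. Ordinary loss to follow-up is the main route. Fitting failure is a further possible one, and complication dismissals are minor.

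**What to change.** In Data Analysis and Sample Size Justification, and in the visit procedures:

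1. Replace the paired t test for multifocal versus single vision with a mixed model (lens, period, sequence, random subject) using every randomised subject with any study-lens score. Treat CISS alike.
2. Give CLDEQ-8 and CISS for the current lens at any exit contact, in person or by phone, as CLDEQ-8 already is at screening. Record the lens and the reason.
3. Report exits by lens and sequence, including randomised subjects who never reached the fitting endpoint.
4. Add a sensitivity analysis that assigns unfavourable scores to the lens worn (or being fitted) at loss when no score exists, over a stated range.

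The cost is two short questionnaires at an exit contact and a change of model. Exit scores may reflect less than 2 weeks' wear and should be flagged. Subjects who cannot be contacted are covered only by item 4. With 69 already enrolled at the last update, item 2 helps only exits still to come; items 1, 3 and 4 can cover the whole trial as far as exit records allow. No change to the clinical dismissal rule is implied.

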Soft, single vision contact lens wearer who do not currently require a reading aid (reading glasses, bifocal, multifocal contact lenses, etc.)		Reports digital device (smart phone, tablet, computer) of at least 3 hours per day
CLDEQ-8 score ≥ 12 points ¹¹		
No ocular surgery/medication history		
Reports digital device (smart phone, tablet, computer) of at least 3 hours per day		

Table 1: Inclusion criterion

c. Measurement/Instrumentation

All measurements and tests performed throughout this study are currently used in routine eye examinations. The risks associated with all study procedures are no more than would be encountered by the subject during a normal eye exam. All subjects will be habitual soft contact lens wearers, so no additional risk will be incurred by subjects when they are fitted into the two study contact lenses. Below is a summary of all vision tests, dry eye tests, binocular vision tests, and contact lens fitting/assessment methods that will be used throughout the study.

Visual Acuity Assessment: Distance (6 meters) visual acuity will be assessed on a high contrast visual acuity chart when the patients wears their habitual contact lenses in each eye. Patients will instructed to read the 20/25 line monocularly. Subjects who cannot read at least 3 of 5 letters on the 20/25 line with each eye will be excluded from the study.

Refractive Error Determination: Inclusion criteria refractive error will be determined using an autorefractor while the patient is not corrected with spectacles or contact lenses. This non-contact, automated instrument measures the subject's spectacle/contact lens prescription. Subjects that do not meet refractive error inclusion criteria (Table 1) will be excluded from the study.

Contact Lens Dry Eye Questionnaire-8 (CLDEQ-8): The CLDEQ-8 is an eight-item questionnaire that has been validated to reflect satisfaction and change in opinion of soft contact lenses.¹¹ To ensure all study subjects are significantly symptomatic for contact lens discomfort, all subjects must have a score ≥12 points (show to be a score that identifies a subject that could benefit from

clinical management of contact lens-related symptoms¹⁵) in order to qualify for the baseline examination.

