Convergence Insufficiency Symptom Survey (CISS): The CISS is a 16-item questionnaire that has been validated to assess symptoms of convergence insufficiency, a common binocular vision disorder.¹⁶ Symptoms of contact lens discomfort and dryness are similar to convergence insufficiency symptoms,⁹ so the CISS will be administered at each study visit.

Binocular Vision Testing: Binocular vision testing assesses the ability of the eyes to move, converge, diverge, and focus together while focusing at distance and near targets. Symptoms of binocular vision disorders are similar and sometimes associated with accommodative disorders. Therefore, we will exclude any subject that has significant signs of a binocular vision disorder. Binocular vision testing for this study will include horizontal heterophoria measurements, near point of convergence (NPC), and accommodative function testing. All of these tests are performed in routine eye exams.

Heterophoria Measurement: Heterophoria measurements how well the eyes simultaneously focus and align together. Several methods exist to measure heterophoria. Modified Thorington (MT) testing has been shown to be the most repeatable form,¹⁷ so it will be used in this study at distance (6 m) and near (40 cm). A Maddox rod (transparent red occluder with cylindrical grooves) will be used to perform the technique. The MT card contacts horizontal and vertical rows of numbers that are calibrated to measure prism diopters at each distance. Each card contains a small central hole where a penlight will be shown through. The subject will hold a Maddox rod over their right eye in a horizontal orientation, and the subject will see a red streak of light while viewing the MT card. At both distance and near, the subject will be asked to report what numbered row the red streak is passing through. This number on the card corresponds to a particular horizontal heterophoria finding, which will be recorded for distance and near. Subjects reporting 4 or more esophoria or exophoria at distance or near will be excluded from the study.

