Pre-presbyopes with symptoms of contact lens discomfort and asthenopia will be recruited from The Ohio State University College of Optometry Clinics. Interested subjects will be instructed to contact investigators by email. The Contact Lens Dry Eye Questionnaire-8 (CLDEQ-8), a survey validated to reflect change in opinion of contact lenses,¹¹ will be administered over the phone to ensure each subject has significant discomfort symptoms. Each subject must have a score of ≥ 12 points¹⁵ to qualify for the first, baseline examination.

At the baseline examination, inclusion criteria will be confirmed. The presence of concurrent dry eye or a binocular vision disorder (a group of disorders that involved how the eyes move together) will confound study results, so subjects with significant signs of these conditions will be excluded from the study (as defined in Table 1). With the each subject's habitual contact lens correction, heterophoria at distance and near and NPC will be measured to determine binocular vision eligibility. Accommodative function will also be assessed at this time. TBUT, ocular surface staining, and Schirmer testing will be performed to determine dry eye eligibility. Keratograph 5M tear imaging will also be performed at this time. A general anterior segment assessment will be made and assessment of the lid margins and Meibomian glands after habitual lens wear will be recorded. The CISS will be administered at the baseline examination. Subjects who meet all inclusion criteria will be enrolled and randomized (blocked randomization design with a 1:1 allocation ratio) to receive either the single vision Bausch + Lomb ULTRA® or single vision Bausch + Lomb ULTRA® for Presbyopia contact lenses first. All subjects who complete the baseline examination (whether enrolled or not) will receive \$40 cash and a parking pass.

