After wearing the first dispensed lens pair for approximately 2 weeks, subjects will return to the clinic. The CLDEQ-8 and CISS will be administered and subjects will be instructed to answer based on their experience with the first dispensed lens pair. Accommodative testing and heterophoria measurements with the first dispensed lens pair will be performed. The lenses will be removed, discarded, and an anterior ocular segment assessment will be performed on both eyes. An assessment of the lid margins and Meibomian glands will be performed. As well, an assessment of the tear film (TBUT, Schirmer test, and ocular surface staining) and tear film assessment with the Keratograph 5M will be performed.

Next, the remaining contact lens (Bausch + Lomb ULTRA® or Bausch + Lomb ULTRA® for Presbyopia, depending on which lens the subject wore first) will be fitted on each subject. Fit, vision, and comfort will be assessed (as in the baseline examination) after the lenses have settled on the eye for 10 minutes. When a satisfactory endpoint is reached, subjects will again be educated on proper lens care (daily lens wear, no sleeping in lenses, proper cleaning/storage with Biotrue® solution) and be given a fresh contact lens case and Biotrue® contact lens solution. Accommodative testing and heterophoria measurements with the second dispensed lens pair will be performed. Each subject will schedule an appointment for the third and final examination approximately 2 weeks from the date of the second examination. Subjects will receive \$40 cash and a parking pass at the end of the second examination.

Third and Final Examination

After wearing the second dispensed lens pair for approximately 2 weeks, subjects will return to the clinic. The CLDEQ-8 and CISS will be administered and subjects will be instructed to answer based on their experience with the second dispensed lens pair. Accommodative testing and heterophoria measurements with the second dispensed lens pair will be performed. The lenses will be removed, discarded, and an anterior ocular segment assessment will be performed on both eyes. An assessment of the lid margins and Meibomian glands will be performed. As well, an assessment of the tear film (TBUT, Schirmer test, and ocular surface staining) and tear film assessment with the Keratograph 5M will be performed.

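### The only habitual-lens CLDEQ-8 described is the telephone screening score (12 or more required); if it is the comparator, two of the three paired t tests favour the study lenses by regression to the mean

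*Combined protocol and SAP*

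**What the plan says.** All references are to the combined protocol and SAP.

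- **Analysis.** Under Data Analysis and Sample Size Justification, paired t "tests will be performed to compare mean CLDEQ-8 scores with habitual single vision lenses", single vision ULTRA and ULTRA for Presbyopia (the multifocal). That makes three pairwise contrasts, two of which use the habitual score. A repeated measures ANOVA on age and myopia uses the same three lens conditions. No contrast is named as primary, and the source of the habitual score is not given.
- **Screening.** Under Measurement/Instrumentation, "all subjects must have a score ≥12 points" "in order to qualify for the baseline examination". Under Subject Enrollment and Baseline Examination and Fitting, the CLDEQ-8 "will be administered over the phone to ensure each subject has significant discomfort symptoms".
- **Baseline visit.** The same section says "The CISS will be administered at the baseline examination", which agrees with the instrument description: "so the CISS will be administered at each study visit". No CLDEQ-8 is listed at this visit. The section also says "At the baseline examination, inclusion criteria will be confirmed".
- **Later visits.** Under Second Examination and Fitting: "The CLDEQ-8 and CISS will be administered and subjects will be instructed to answer based on their experience with the first dispensed lens pair". The third examination does the same for the second pair. Neither later score has a threshold.

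**The concern.** A higher CLDEQ-8 means worse symptoms. If the habitual score is the one on which subjects were selected, it is cut off from below while the two study-lens scores are not. Part of a high qualifying score is transient, so the next score falls on average even if the lens changes nothing. Both habitual-versus-study tests would then lean toward the study lens.

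These two tests are unrandomised in any case, because habitual lenses always come first. If the telephone score is the comparator, they also mix telephone with clinic administration.

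With no primary contrast named, a significant multifocal-versus-habitual difference could be reported as relief due to the multifocal. In the ANOVA, the habitual level would carry the same shift into any lens effect. The August 2017 sample size update already relies on a change in CLDEQ-8 without saying which reading the change starts from.

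**Working it through.** **Which reading is the habitual score?** The CISS is placed at every visit and again explicitly at baseline. The CLDEQ-8 is placed on the telephone and at the second and third examinations. On the text, the telephone score is the only habitual-lens reading available. The general statement about confirming inclusion criteria could cover a repeat, and Figure 1 is not reproduced in the text available, so a repeat cannot be excluded.

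**Inputs from the documents.** The plan gives no figure for this bias to reproduce, and no CLDEQ-8 mean, SD or retest correlation. What it does give is the cut-off (12), the assumed loss (20%) and the enrolment position at 11/21/2017: 69 enrolled, 15 of the 30 additional subjects among them. Still to enrol: 30 − 15 = 15. Total: 69 + 15 = 84. Completers: 84 × 0.8 = 67.2, about 67.

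**Assumptions.** Scores are normal with equal mean and SD on each occasion. There is no true lens effect. The correlation r between the screening score and a later score, among all those screened, is 0.9 to 0.5.

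**Formulas**, with c the cut-off in SD units from the mean of all those screened:

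- λ = φ(c) / (1 − Φ(c))
- spurious fall = (1 − r) λ
- SD of the difference = √[(1 − r)²(1 + cλ − λ²) + (1 − r²)]
- probability of a significant result favouring the study lens: noncentral t with n − 1 degrees of freedom and noncentrality √n × fall / SD of the difference, beyond the upper 2.5% point.

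**Example, c = −1, r = 0.5, n = 67.** λ = 0.2420 / 0.8413 = 0.288. Fall = 0.5 × 0.288 = 0.144 SD. SD of the difference = √(0.25 × 0.630 + 0.75) = 0.953. The ratio is 0.151, the noncentrality is 0.151 × √67 = 1.24, and the probability is 0.229. With r = 0.9 the fall is 0.029, the SD of the difference 0.443 and the probability 0.075.

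| Cut-off relative to mean of those screened | Screened out | Spurious fall (SD), r = 0.9 to 0.5 | False improvement, n = 67 | Same, n = 45 |
|---|---|---|---|---|
| −2 SD | 2% | 0.006 to 0.028 | 3-4% | 3-4% |
| −1 SD | 16% | 0.029 to 0.144 | 7.5-23% | 6-17% |
| at the mean | 50% | 0.080 to 0.399 | 31-94% | 22-81% |

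The n = 45 column uses the plan's sample size before loss. A fixed bias reaches significance more often as n grows, so the larger current enrolment makes matters somewhat worse.

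**Randomised contrast.** Neither study-lens score was used for selection. In simulations with no true effect at n = 45, multifocal versus single vision rejected in 4.3% to 5.3% of trials, two-sided, as it should.

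**If there was a baseline repeat.** A repeat not used for eligibility removes the bias: simulated one-sided rejection was 2.2% to 2.9%. A repeat that also had to reach 12 would leave a smaller shift. Over cut-offs from −2 to +0.5 SD it is 0.003 to 0.42 SD, against 0.006 to 0.57 SD for the telephone score.

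**The case against.** The strongest reply is that the premise is unproven. A score of 12 or more is a Table 1 criterion, criteria are confirmed at baseline, and the flow chart cannot be read here. That stands, and it is why the point is conditional. It does not clear the plan: no repeat is stated, and the analysis section does not say which reading is used. Nor do the baseline failures settle the matter. The first 9 are put down to dry eye and binocular vision criteria, but no reasons are given for the other 26 of the 35.

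A second reply is that a range from 3% to 94% cannot separate a trivial problem from a serious one. That also stands. The section on enrolment says that symptomatic wearers are recruited, so the lower cut-offs may be more plausible, and nothing in the documents shows that half of the callers were screened out.

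Three stronger readings are tempting, and the documents support none of them:

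- A reader might infer that the telephone score is certainly the comparator. The plan does not say so.
- A reader might infer that the trial's test of multifocal correction is biased. The masked, randomised contrast between the two study lenses is not touched.
- A reader might infer that the age interaction behind the August 2017 increase is an artefact. Age or myopia interactions are affected only if the shift differs by age or myopia, and nothing shows that it does.

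The CISS, analysed in the same way, was not used for selection and could be affected only through its correlation with the CLDEQ-8.

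**Conclusion.** The concern holds conditionally. If the telephone score supplies the habitual CLDEQ-8, regression to the mean biases the habitual-versus-single-vision and habitual-versus-multifocal tests toward the study lenses. The direction needs only a retest correlation below 1 and a cut-off that excludes some callers. The size is undetermined: the rates in the table rest on assumed normal scores, assumed correlations, an assumed position of the cut-off and about 67 completers. Whatever the source of the habitual score, these two contrasts are uncontrolled before-after comparisons. This should be fixed, but it does not threaten the randomised comparison.

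**What to change.** 1. Base the efficacy conclusion on multifocal versus single vision ULTRA. Disclose that this contrast was designated after the August 2017 look at the data, since naming it now is post hoc.
2. State which habitual CLDEQ-8 reading is used, including for any change score. If it is the screening score, draw no lens-effect conclusion from habitual-versus-study differences. Show habitual scores as descriptive baseline data with an explicit caveat on regression to the mean, and report the share of telephone screens below 12, which indicates where the trial sits in the table. Replacing p values with confidence intervals is not enough, because an interval around the same difference carries the same bias.
3. Base the repeated measures ANOVA conclusions on the two study lenses.

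The cost is wording in the analysis plan plus a count of telephone screens. No new visits or procedures are needed. The downside is that the habitual comparisons are no longer inferential.
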